APPENDIX 8 DEATH

At any time during the assessment period, if a death event occurs, a dossier package with medical records, imaging data, laboratory studies and any other relevant medical information should be created.

Deaths will be classified as

A. VTE-related Death:

[figure not shown]
- (1) Fatal pulmonary embolism
 - (a) Autopsy reveals major pulmonary embolism (occlusion of at least two segmental pulmonary arteries or their equivalent), or
 - (b) Clinical course is compatible with pulmonary embolism AND there is not a more compelling alternative diagnosis to account for death.
- (2) Fatal non-hemorrhagic stroke related to **paradoxical embolus**: ischemic stroke with the presence of venous thromboembolism and a right-to-left shunt (eg, patent foramen ovale, a pulmonary fistul) revealed by imaging, surgery or autopsy.
- (3) Fatal MI related to **paradoxical embolus**: acute MI with the presence of venous thromboembolism and a right-to-left shunt (eg, patent foramen ovale, a pulmonary fistul) revealed by imaging, surgery or autopsy.

[figure not shown]
B. Fatal Bleeding

[figure not shown]
- (a) Death will be classified as related to fatal bleeding if there is overt bleeding (including autopsy evidence) AND there is not a more compelling alternative diagnosis to account for death.
- (b) Death associated with pulmonary hemorrhage will usually be attributed to underlying pulmonary embolism.

[figure not shown]
C. Other (eg, malignancy, infection, tumor lysis syndrome, cardiovascular – related, respiratory failure – related , central nervous system (CNS) – related, withdrawal of support, study drug toxicity other than bleeding (specify), and Other not mentioned).

[figure not shown]
D. Unknown Cause: No data are available to assign a cause of death.

[figure not shown]

[figure not shown]

[figure not shown]

[figure not shown]

[figure not shown]

[figure not shown]

APPENDIX 10 COMMON STRONG INHIBITORS OF BOTH CYTOCHROME P450 3A4 (CYP3A4) AND P-GLYCOPROTEIN (P-GP) (NOT ALL INCLUSIVE)²⁶

Apixaban is hepatically metabolized by cytochrome P-450 3A4 (CYP3A4) and is a substrate for the efflux transporter P-glycoprotein (P-GP). Co-administration of drugs that are strong inhibitors of both CYP3A4 and P-GP can increase apixaban blood concentrations. Patients with renal insufficiency or of low body weight may be at increased risk of excessive anticoagulation due to CYP and P-gp drug interactions, and avoidance of certain drug combinations should be considered.

Examples of strong inhibitors of CYP3A4 are prohibited while subjects are on treatment with BMS-562247. Some examples of strong inhibitors of CYP3A4 are:

Clarithromycin	nelfinavir
telithromycin	ritonavir
itraconazole	saquinavir
ketoconazole	indinavir
voriconazole	cobicistat
posaconazole	

Strong inducers of P-gp and CYP3A4 are expected to decrease apixaban blood concentrations and can result in failure of therapeutic anticoagulant effect.

Examples of strong inducers of both CYP3A4 and P-gp are:

Rifampin	phenytoin
carbamazepine	St. John's wort

These lists are not meant to be all inclusive. Please consult individual drug labels for further information.

Management suggestions:

Avoid co-administration of strong inhibitors of both CYP3A4 and P-gp. Bleeding risk is expected to be further increased in patients with renal insufficiency, depending upon severity.

The efficacy of routine coagulation testing to evaluate the degree of anticoagulation with apixaban is limited.

Avoid co-administration of strong inducers of both CYP34 and P-gp.

APPENDIX 11 COMMON NONSTEROIDAL ANTI-INFLAMMATORY DRUGS (NSAIDS) (NOT ALL INCLUSIVE)

Over-the-Counter NSAIDS

BRAND NAME	GENERIC NAME
Advil, Motrin	ibuprofen
Aleve	naproxen sodium
Ascriptin, Bayer, Ecotrin	aspirin

Prescription NSAIDS

BRAND NAME	GENERIC NAME
Anaprox	naproxen sodium
Celebrex	celecoxib
Clinoril	sulindac
Daypro	oxaprozin
Disalcid	salsalate
Dolobid	diflunisal
Feldene	piroxicam
Indocin	indomethacin
Lodine	etodolac
Mobic	meloxicam
Naprosyn	naproxen
Relafen	nabumetone
Toradol	ketorolac tromethamine
Vimovo	naproxen/esomeprazole
Voltaren	diclofenac

APPENDIX 12 OUTLINE OF CHILDREN'S ONCOLOGY GROUP (COG) INDUCTION THERAPY PHASE IA

Table 6: Outline of Children's Oncology Group (COG) Induction Therapy Phase IA				
DRUG	ROUTE	DOSAGE	DAYS	IMPORTANT NOTES
Intrathecal Cytarabine (IT ARAC)	IT	Age (yrs) → Dose 1-1.99 → 30 mg 2-2.99 → 50 mg ≥ 3 → 70 mg	Given at time of diagnostic lumbar puncture (LP) OR Day 1 ^a	Note age-based dosing
VinCRISTine (VCR)	IV push over 1 minute+	1.5 mg/m ² /dose	Days 1, 8, 15 & 22	+Or infusion via minibag as per institutional policy Maximum dose: 2 mg
Dexamethasone (DEX) Patients < 10 years ONLY	PO (may be given IV)	5 mg/m ² /dose BID	Days 1 - 14	Total daily dose: 10 mg/m ² /day, divided BID
PredniSONE (PRED) Patients ≥ 10 years ONLY	PO (may be given IV)	30 mg/m ² /dose BID	Days 1 - 28	Total daily dose: 60 mg/m ² /day, divided BID Note: IV methylprednisolone may be substituted for oral predniSONE at 80% of the dose
DAUNOrubicin (DAUN)	IV push over 1-15 minutes	25 mg/m ² /dose	Days 1, 8, 15 & 22	
Pegaspargase (PEG-ASP)	IV over 1-2 hours	2500 International Units/m ²	Day 4	Note: pegaspargase must be administered on Day 4. Administer through the tubing of a freely infusing solution of D5W or 0.9% NaCl
Intrathecal Methotrexate (IT MTX)	IT	Age (yrs) → Dose 1-1.99 → 8 mg 2-2.99 → 10 mg 3-8.99 → 12 mg ≥ 9 → 15 mg	Days 8 & 29 CNS3 also on Days 15 & 22	Note age-based dosing

^a On Day 1 OR at the time of diagnostic lumbar puncture (LP) if < than 72 hours from the start of protocol therapy.

APPENDIX 13 GFR ASSESSMENT

Inadequate renal function is defined as <30% of 1 standard deviation (SD) below normal GFR for age and size as determined by the Schwartz formula [$eGFR \text{ (ml/min/1.73m}^2\text{)} = 0.413 * (\text{height (cms)}/\text{serum creatinine (mg/dL)})$]. If serum creatinine concentration is measured in SI units (umoles/L), divide this number by the conversion factor of 88.4 to get the SI units (mg/dL) before inserting into the Schwartz formula to calculate eGFR.

Table 7: GFR Assessment		
Age (sex)	Normal GFR (for reference only. Not for study qualification) (Mean GFR ± SD) (mL/min/1.73m²)	GFR for study qualification^a (Mean GFR) (mL/min/1.73m²)
1 week (males and females)	41 ± 15	≥ 8
2 - 8 weeks (males and females)	66 ± 25	≥ 12
> 8 weeks to < 2 years (males and females)	96 ± 22	≥ 22
2 - 12 years (males and females)	133 ± 27	≥ 30
13 - 17 years (males)	140 ± 30	≥ 30
13 - 17 years (females)	126 ± 22	≥ 30
1 week (males and females)	41 ± 15	≥ 8
2 - 8 weeks (males and females)	66 ± 25	≥ 12

^a Patient may be enrolled if GFR is at or greater to this value as determined by Schwartz formula²⁷

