3.3.1 Inclusion Criteria

1. Signed Written Informed Consent

- a. Signed written informed consent obtained from subject's legally acceptable representative (parents or guardians) according to local regulations and if mentally capable, assent from subject if required locally

2. Target Population

- a. New diagnosis of de novo ALL, or lymphoblastic lymphomas (T or B cell)
- b. Planned 3-4 drug systemic induction chemotherapy with a corticosteroid, vincristine and a single dose or multiple doses of asparaginase, with or without daunorubicin
- c. Patients with mixed-phenotype acute leukemia (MPAL) who will be treated with ALL induction chemotherapy as described above (Inclusion 2b) are also eligible
- d. Functioning CVAD, defined as no known mechanical problem and including external tunneled CVAD, implantable ports, and peripherally inserted central catheters (PICC) placed in a new location between Day -7 and Day 4±3 of induction chemotherapy and planned to remain in place until at least Day 29±5 days of induction. The CVAD must be

inserted prior to the start of study medication and could be inserted prior to signing informed consent as part of standard of care.

Note: The CVAD can be replaced if it is a planned replacement (eg, it is allowed to have a PICC at the time of enrollment that will be changed to a more permanent line later in induction); and it is allowed if a CVAD is not in place at the time of enrollment as long as it is in place before apixaban starts.

- e. Not applicable per protocol amendment 04
- f. Able to tolerate oral medication or have it administered via an NGT or GT tube.
- g. Subject Re-enrollment: This study permits re-enrollment of a subject that has previously failed screening but currently meets entry criteria. If re-enrolled, the subject must be re-consented and receive a new patient identification number.

3. Age and Reproductive Status

- a. Males and females, age ≥ 1 year (365 days) to < 18 (17 years and 364 days) years at the time of consent.

Females of reproductive potential (FRP) must have a negative serum or urine pregnancy test (minimum sensitivity 25 IU/L or equivalent units of HCG) at screening.

For all FRP that will be inpatients from consenting to the first dose of apixaban, a negative pregnancy test must be recorded in the subject's hospital chart prior to receiving the first dose of apixaban.

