3.3.2 Exclusion Criteria

1. Target Disease Exceptions

- a. Not applicable per protocol Amendment 02
- b. Subject scheduled to have > 3 LP's over the course of the study treatment period, ie. Day of Randomization to Day 29 visit

1. Medical History and Concurrent Diseases

- a. Prior history of documented DVT or PE in the past 3 months
- b. Known inherited bleeding disorder or coagulopathy with increased bleeding risk (eg, hemophilia, von Willebrand disease, etc.)
- c. Major surgery (excluding CVAD replacement and bone marrow aspiration and non-open biopsy) within the last 7 days prior to enrollment that may be associated with an increase in the risk of bleeding. Open biopsy is considered a major surgery.
- d. Active clinically significant bleeding
- e. Known inherited or acquired antiphospholipid syndrome [APS]

2. Physical and Laboratory Test Findings

- a. Uncontrolled severe hypertension at enrollment. Severe hypertension is defined as a systolic or diastolic blood pressure (BP) > 5 mm Hg above the 95th percentile as defined by the National High Blood Pressure Education Program Working Group (NHBPEP) established guidelines for the definition of normal and elevated blood pressures in children. See [Appendix 14](#) for references.⁵⁷

Note: Subjects with a blood pressure (BP) > 95th percentile for age, height, and gender which is not life-threatening can be enrolled, provided their hypertension is treated as deemed appropriate by the investigator per standard of care.

- b. Extreme hyperleukocytosis, white blood cell (WBC) counts over 200 x 10⁹/L (200,000/microL) at the time of enrollment.

Note: Subjects with WBC counts over 200 x 10⁹/L (200,000/microL) at the time of diagnosis can be enrolled if their WBC counts decreased to 200 x 10⁹/L or below at the time of enrollment, except subjects who have had leukopheresis, these subjects will be excluded regardless of WBC count.

- c. Liver dysfunction manifested by SGPT (ALT) > 5X ULN and/or AST > 5X ULN and/or direct (conjugated) bilirubin > 2X ULN (subjects with a total bilirubin value ≤ 2XULN can be enrolled if the direct bilirubin values are not available)
- d. Renal function < 30% of normal for age and size as determined by the Schwartz formula: [eGFR (ml/min/1.73 m²) = 0.413 * (height (cm) / serum creatinine (mg/dl)] (See [Appendix 13](#)).

Note: Liver and renal function tests obtained within 1 week prior to enrollment are acceptable.

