5 STUDY ASSESSMENTS AND PROCEDURES

5.1 Flow Chart/Time and Events Schedule

Table 5.1-1: Screening Procedural Outline ACCL1333 / CV185155			
Procedure	Consent/Screening Visit^a Day -7 to 4±3	Randomization Visit^a Day 1 to 4±3	Notes
Eligibility Assessments			
Informed Consent/Assent	X		Informed consent/assent must be signed prior to initiating any study procedures.
Inclusion/Exclusion Criteria	X	X	
Medical History	X		
Physical Measurements	X		Height, Body Weight, and calculated Body Mass Index
Catheter History	X		
Concomitant Medication Assessment	X	X	Medications taken at the time of signing the informed consent and after signing the informed consent must be recorded on the appropriate CRF page
Safety Assessments			
Full Physical Examination	X		Includes assessment of signs of venous thromboembolism or bleeding.
Vital Signs	X		Heart rate, BP, respiratory rate and temperature
Adverse Events Assessment		X	Collection of SAEs begins after signed consent; Collection of non-serious AE begins after randomization

Table 5.1-1: Screening Procedural Outline ACCL1333 / CV185155			
Procedure	Consent/Screening Visit^a Day -7 to 4±3	Randomization Visit^a Day 1 to 4±3	Notes
Laboratory Tests	X		CBC with platelets, ALT, AST, conjugated bilirubin, serum creatinine, PT (if available), aPTT and INR (Total bilirubin is acceptable if it is normal. Conjugated bilirubin should be obtained if total bilirubin is high). Renal function must be > 30% of normal for age and size. A platelet count ≥ 20 x 10 ⁹ per L must be obtained within 24 hours prior to starting apixaban. Screening labs as part of the standard of care obtained within 1 week prior to signing the informed consent can be used
Laboratory Tests during LP WBC and RBC in CSF	X	X	WBC and RBC in CSF required only once
Pregnancy Test FRP only	X		Negative serum or urine pregnancy test (minimum sensitivity 25 IU/L or equivalent units of HCG) for FRP.
Clinical Drug Supplies			
Dispense Study Drug		X	Study medication must be initiated prior to or within 12 hours of the first dose of asparaginase or by Day 4±3 of induction chemotherapy, whichever is first
Enroll via IVRS	X		
Randomize via IVRS		X	Randomization occurs between Day 1 and 4±3 of planned 3-4 drug systemic induction chemotherapy. Subjects can be enrolled and randomized during the same visit.

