5.3.5 Creatinine Clearance

Based on the results of the enrollment visit clinical laboratory tests, eGFR will be estimated based on the Schwartz formula (See [Table 5.1-1](#) for timing of assessments and [Appendix 13](#) for eGFR assessment).

Inadequate Renal Function < 30% of normal for age and size as determined by the Schwartz formula⁶⁸ [eGFR (ml/min/1.73m²) = 0.413 * (height (cms) / serum creatinine (mg/dl)). If serum creatinine concentration is measured in SI units (umoles/L), divide this number by the conversion

factor of 88.4 to get the SI units (mg/dl) before inserting into the Schwartz formula to calculate eGFR]. Subjects are required to have an eGFR > 30% of normal for age and size to be enrolled in the study.

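### The renal eligibility cut-off is stated inconsistently: from age 2, the Appendix 13 table admits children whom the appendix's own definition calls inadequate

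*Protocol*

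**What the plan says.** The renal criterion appears in five places in the protocol.

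- **Synopsis (exclusion e) and Section 3.3.2.** The exclusion is "Renal function < 30% of normal for age and size as determined by the Schwartz formula". Section 3.3.2 adds a reference to Appendix 13. Neither place gives a number or an SD term.
- **Table 5.1-1.** "Renal function must be > 30% of normal for age and size".
- **Section 5.3.5.** "Subjects are required to have an eGFR > 30% of normal for age and size to be enrolled in the study". The same section calls function below 30% inadequate and refers to Appendix 13 for the eGFR assessment.
- **Appendix 13, text.** "Inadequate renal function is defined as <30% of 1 standard deviation (SD) below normal GFR for age and size".
- **Appendix 13, Table 7.** One column gives the mean and SD of normal GFR by age and sex, and its header marks it as reference information that is not to be used for qualification. The next column gives the qualifying values: at least 22 for the row that ends below 2 years, and at least 30 for each row from 2 to 17 years. The footnote reads "Patient may be enrolled if GFR is at or greater to this value as determined by Schwartz formula".

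The age criterion in Section 3.3.1 is "Males and females, age ≥ 1 year (365 days) to < 18 (17 years and 364 days) years at the time of consent", so four rows of Table 7 matter: over 8 weeks to under 2 years, 2-12 years, males 13-17 and females 13-17.

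**The concern.** A safety exclusion should come down to one number per child. Here the main text refers to normal, the appendix text to one SD below normal, and the table to fixed values. If these disagree, two sites can each follow the protocol and reach opposite decisions on the same child.

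The screening decision carries weight in this design. Serum creatinine is a screening test in Table 5.1-1 and is not in the on-treatment laboratory row of Table 5.1-2. Section 4.5 does not permit dose modifications. Section 3.3.2 closes by insisting that all eligibility criteria be met in full. Under SAP Section 7.2.1, departures from important eligibility criteria are reported as important protocol deviations, so whether a borderline child counts as a deviation could depend on which passage is applied.

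**Working it through.** **Inputs.** The means, SDs and qualifying values are from Table 7 (mL/min/1.73m²). The 30% is from all five places.

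**Step 1: try to reproduce the table from the appendix definition**, read as 0.30 × (mean − SD).

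| Row | Mean ± SD | 0.30 × (mean − SD) | Table 7 | Agrees after rounding? |
|---|---|---|---|---|
| >8 weeks to <2 y | 96 ± 22 | 0.30 × 74 = 22.2 | 22 | yes |
| 2-12 y | 133 ± 27 | 0.30 × 106 = 31.8 | 30 | no, 1.8 apart |
| 13-17 y males | 140 ± 30 | 0.30 × 110 = 33.0 | 30 | no, 3.0 apart |
| 13-17 y females | 126 ± 22 | 0.30 × 104 = 31.2 | 30 | no, 1.2 apart |

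The two infant rows, outside the trial's age range, also agree: 0.30 × (41 − 15) = 7.8, tabled as 8, and 0.30 × (66 − 25) = 12.3, tabled as 12. The formula therefore appears to be the one behind the younger rows. From age 2 it exceeds the tabled value by 6.0%, 10.0% and 4.0% of 30, which rounding to a whole number cannot explain.

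**Step 2: try other readings.** In the order of the table above, 0.30 × (mean − 2 SD) gives 15.6, 23.7, 24.0 and 24.6, and 0.30 × SD gives 6.6, 8.1, 9.0 and 6.6. Neither fits. The smaller of 30 and 0.30 × (mean − SD), rounded, fits every row, but no cap at 30 is stated.

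**Step 3: the conflict that needs no assumption about the main text.** These eGFR values are inadequate by the appendix text and qualify by its table:

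- 2-12 years: 30 to below 31.8
- males 13-17: 30 to below 33.0
- females 13-17: 30 to below 31.2

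At ages 1 to under 2 only the rounding sliver from 22 to below 22.2 is affected.

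**Step 4: the main text, under a stated assumption.** If normal means the Table 7 mean, 30% of it is:

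| Row | 0.30 × mean | Gap to Table 7 | Part due to SD term (0.30 × SD) | Remainder |
|---|---|---|---|---|
| <2 y | 28.8 | 6.8 | 6.6 | 0.2 |
| 2-12 y | 39.9 | 9.9 | 8.1 | 1.8 |
| 13-17 y males | 42.0 | 12.0 | 9.0 | 3.0 |
| 13-17 y females | 37.8 | 7.8 | 6.6 | 1.2 |

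Most of this wider gap comes from normal versus one SD below normal. The flat 30 adds only the remainder from age 2 up.

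**Step 5: the boundary.** The synopsis and Section 3.3.2 exclude below 30%, so exactly 30% is eligible, which agrees in sign with the at-or-above rule in Table 7. Table 5.1-1 and Section 5.3.5 require more than 30%. Section 5.3.5 also calls below 30% inadequate, so a child at exactly 30% is neither inadequate nor enrollable there.

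**The case against.** The best reply is that the protocol has a working rule. Section 3.3.2 refers to Appendix 13, whose Table 7 has a column for study qualification and a footnote permitting enrolment at or above the listed value. A site that follows the reference reaches one number per age group. On this view normal in the main text is shorthand for the appendix definition, which leaves two cut-offs rather than three.

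Much of this stands. In particular, a reader might infer that an 8-year-old with an eGFR of 35 is excluded by Section 3.3.2 and let in by the table. The documents do not support that as fact. The main text gives no figure and refers to the appendix, and the mean that would produce 39.9 is in the column marked as not for qualification. By both Appendix 13 statements the child qualifies (35 is above 31.8 and above 30).

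A reader might also take Appendix 10 as evidence that enrolling at these eGFR values raises bleeding risk. Its sentence, "Bleeding risk is expected to be further increased in patients with renal insufficiency, depending upon severity", comes directly after advice to avoid strong inhibitors of both CYP3A4 and P-gp, which Section 3.4.1 prohibits. It concerns that interaction and says nothing about an enrolment threshold.

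The boundary difference matters only at exact equality.

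The reply fails on one point. The cross-reference leads to an appendix that contradicts itself. For a child aged 2-12 with an eGFR of 31, its text and its table give opposite answers however normal is read.

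**Conclusion.** Wrong as written. From age 2, the Table 7 qualifying value of 30 does not follow from the Appendix 13 definition, which gives 31.8, 33.0 and 31.2. The main text omits the SD term altogether, and the boundary sign is not uniform.

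The certain size is 1.2 to 3.0 mL/min/1.73m², confined to ages 2 and over. This takes the appendix wording to mean 30% of (mean − SD), the only stated rule tried that reproduces the younger rows. The larger gap of 6.8 to 12.0 depends on reading normal as the Table 7 mean and should be reported only with that condition.

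It would be too strong to say that the whole table departs from its formula, since the row for ages 1 to under 2 agrees after rounding. It would also be too strong to say that the percentage definition is right and the table wrong: an intended but unstated cap at 30 would explain every row, and the documents do not settle it.

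The documents give no count of affected children; they are probably few. Sample size, power and the primary analysis do not depend on this threshold. Renal function is not among the relevant deviations in SAP Section 7.2.1, so the Evaluable population does not depend on it either.

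**What to change.** Reconcile the synopsis, Section 3.3.2, Section 5.3.5, Table 5.1-1 and Appendix 13 to one stated definition of the renal threshold.

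- Say what normal refers to (the mean, one SD below it, or the tabled value).
- Make the Appendix 13 definition and the Table 7 values agree. If a cap at 30 is intended, state it.
- Use one boundary sign throughout.

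Which threshold is right is a clinical decision for the sponsor.

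The cost is a wording amendment. A few borderline children may change eligibility, depending on the rule chosen. No statistical analysis needs to change.

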APPENDIX 14 BLOOD PRESSURE (BP) LEVELS FOR GIRLS AND BOYS BY AGE AND HEIGHT PERCENTILE ²⁸

Instructions for using this BP Chart:

- 1) Measure the patient's blood pressure using an appropriate size cuff.
- 2) Select appropriate chart for a female or male patient.
- 3) Using the "age" row and "height" column determine if the BP is within the ULN.

BP Levels for Boys by Age and Height Percentile

Age, y	BP Percentile	SBP, mm Hg								DBP, mm Hg							
		Percentile of Height								Percentile of Height							
		5th	10th	25th	50th	75th	90th	95th	5th	10th	25th	50th	75th	90th	95th		
1	50th	80	81	83	85	87	88	89	34	35	36	37	38	39	39		
	90th	94	95	97	99	100	102	103	49	50	51	52	53	53	54		
	95th	98	99	101	103	104	106	106	54	54	55	56	57	58	58		
	99th	105	106	108	110	112	113	114	61	62	63	64	65	66	66		
2	50th	84	85	87	88	90	92	92	39	40	41	42	43	44	44		
	90th	97	99	100	102	104	105	106	54	55	56	57	58	58	59		
	95th	101	102	104	106	108	109	110	59	59	60	61	62	63	63		
	99th	109	110	111	113	115	117	117	66	67	68	69	70	71	71		
3	50th	86	87	89	91	93	94	95	44	44	45	46	47	48	48		
	90th	100	101	103	105	107	108	109	59	59	60	61	62	63	63		
	95th	104	105	107	109	110	112	113	63	63	64	65	66	67	67		
	99th	111	112	114	116	118	119	120	71	71	72	73	74	75	75		
4	50th	88	89	91	93	95	96	97	47	48	49	50	51	51	52		
	90th	102	103	105	107	109	110	111	62	63	64	65	66	66	67		
	95th	106	107	109	111	112	114	115	66	67	68	69	70	71	71		
	99th	113	114	116	118	120	121	122	74	75	76	77	78	78	79		
5	50th	90	91	93	95	96	98	98	50	51	52	53	54	55	55		
	90th	104	105	106	108	110	111	112	65	66	67	68	69	69	70		
	95th	108	109	110	112	114	115	116	69	70	71	72	73	74	74		
	99th	115	116	118	120	121	123	123	77	78	79	80	81	81	82		
6	50th	91	92	94	96	98	99	100	53	53	54	55	56	57	57		
	90th	105	106	108	110	111	113	113	68	68	69	70	71	72	72		
	95th	109	110	112	114	115	117	117	72	72	73	74	75	76	76		
	99th	116	117	119	121	123	124	125	80	80	81	82	83	84	84		
7	50th	92	94	95	97	99	100	101	55	55	56	57	58	59	59		
	90th	106	107	109	111	113	114	115	70	70	71	72	73	74	74		
	95th	110	111	113	115	117	118	119	74	74	75	76	77	78	78		
	99th	117	118	120	122	124	125	126	82	82	83	84	85	86	86		
8	50th	94	95	97	99	100	102	102	56	57	58	59	60	60	61		
	90th	107	109	110	112	114	115	116	71	72	72	73	74	75	76		
	95th	111	112	114	116	118	119	120	75	76	77	78	79	79	80		
	99th	119	120	122	123	125	127	127	83	84	85	86	87	87	88		
9	50th	95	96	98	100	102	103	104	57	58	59	60	61	61	62		
	90th	109	110	112	114	115	117	118	72	73	74	75	76	76	77		
	95th	113	114	116	118	119	121	121	76	77	78	79	80	81	81		
	99th	120	121	123	125	127	128	129	84	85	86	87	88	88	89		
10	50th	97	98	100	102	103	105	106	58	59	60	61	61	62	63		
	90th	111	112	114	115	117	119	119	73	73	74	75	76	77	78		
	95th	115	116	117	119	121	122	123	77	78	79	80	81	81	82		
	99th	122	123	125	127	128	130	130	85	86	86	88	88	89	90		
11	50th	99	100	102	104	105	107	107	59	59	60	61	62	63	63		
	90th	113	114	115	117	119	120	121	74	74	75	76	77	78	78		
	95th	117	118	119	121	123	124	125	78	78	79	80	81	82	82		
	99th	124	125	127	129	130	132	132	86	86	87	88	89	90	90		
12	50th	101	102	104	106	108	109	110	59	60	61	62	63	63	64		
	90th	115	116	118	120	121	123	123	74	75	75	76	77	78	79		
	95th	119	120	122	123	125	127	127	78	79	80	81	82	82	83		
	99th	126	127	129	131	133	134	135	86	87	88	89	90	90	91		
13	50th	104	105	106	108	110	111	112	60	60	61	62	63	64	64		
	90th	117	118	120	122	124	125	126	75	75	76	77	78	79	79		
	95th	121	122	124	126	128	129	130	79	79	80	81	82	83	83		
	99th	128	130	131	133	135	136	137	87	87	88	89	90	91	91		
14	50th	106	107	109	111	113	114	115	60	61	62	63	64	65	65		
	90th	120	121	123	125	126	128	128	75	76	77	78	79	79	80		
	95th	124	125	127	128	130	132	132	80	80	81	82	83	84	84		
	99th	131	132	134	136	138	139	140	87	88	89	90	91	92	92		
15	50th	109	110	112	113	115	117	117	61	62	63	64	65	66	66		
	90th	122	124	125	127	129	130	131	76	77	78	79	80	80	81		
	95th	126	127	129	131	133	134	135	81	81	82	83	84	85	85		
	99th	134	135	136	138	140	142	142	88	89	90	91	92	93	93		
16	50th	111	112	114	116	118	119	120	63	63	64	65	66	67	67		
	90th	125	126	128	130	131	133	134	78	78	79	80	81	82	82		
	95th	129	130	132	134	135	137	137	82	83	83	84	85	86	87		
	99th	136	137	139	141	143	144	145	90	90	91	92	93	94	94		
17	50th	114	115	116	118	120	121	122	65	66	66	67	68	69	70		
	90th	127	128	130	132	134	135	136	80	80	81	82	83	84	84		
	95th	131	132	134	136	138	139	140	84	85	86	87	87	88	89		
	99th	139	140	141	143	145	146	147	92	93	93	94	95	96	97		

The 90th percentile is 1.28 SD, the 95th percentile is 1.645 SD, and the 99th percentile is 2.326 SD over the mean. For research purposes, the SDs in Table B1 allow one to compute BP Z scores and percentiles for boys with height percentiles given in Table 3 (ie, the 5th, 10th, 25th, 50th, 75th, 90th, and 95th percentiles). These height percentiles must be converted to height Z scores given by: 5% = -1.645; 10% = -1.28; 25% = -0.68; 50% = 0; 75% = 0.68; 90% = 1.28; and 95% = 1.645, and then computed according to the methodology in steps 2 through 4 described in Appendix B. For children with height percentiles other than these, follow steps 1 through 4 as described in Appendix B.

BP Levels for Girls by Age and Height Percentile

Age, y	BP Percentile	SBP, mm Hg								DBP, mm Hg							
		Percentile of Height								Percentile of Height							
		5th	10th	25th	50th	75th	90th	95th	5th	10th	25th	50th	75th	90th	95th		
1	50th	83	84	85	86	88	89	90	38	39	39	40	41	41	42		
	90th	97	97	98	100	101	102	103	52	53	53	54	55	55	56		
	95th	100	101	102	104	105	106	107	56	57	57	58	59	59	60		
	99th	108	108	109	111	112	113	114	64	64	65	65	66	67	67		
2	50th	85	85	87	88	89	91	91	43	44	44	45	46	46	47		
	90th	98	99	100	101	103	104	105	57	58	58	59	60	61	61		
	95th	102	103	104	105	107	108	109	61	62	62	63	64	65	65		
	99th	109	110	111	112	114	115	116	69	69	70	70	71	72	72		
3	50th	86	87	88	89	91	92	93	47	48	48	49	50	50	51		
	90th	100	100	102	103	104	106	106	61	62	62	63	64	64	65		
	95th	104	104	105	107	108	109	110	65	66	66	67	68	68	69		
	99th	111	111	113	114	115	116	117	73	73	74	74	75	76	76		
4	50th	88	88	90	91	92	94	94	50	50	51	52	52	53	54		
	90th	101	102	103	104	106	107	108	64	64	65	66	67	67	68		
	95th	105	106	107	108	110	111	112	68	68	69	70	71	71	72		
	99th	112	113	114	115	117	118	119	76	76	76	77	78	79	79		
5	50th	89	90	91	93	94	95	96	52	53	53	54	55	55	56		
	90th	103	103	105	106	107	109	109	66	67	67	68	69	69	70		
	95th	107	107	108	110	111	112	113	70	71	71	72	73	73	74		
	99th	114	114	116	117	118	120	120	78	78	79	79	80	81	81		
6	50th	91	92	93	94	96	97	98	54	54	55	56	56	57	58		
	90th	104	105	106	108	109	110	111	68	68	69	70	70	71	72		
	95th	108	109	110	111	113	114	115	72	72	73	74	74	75	76		
	99th	115	116	117	119	120	121	122	80	80	80	81	82	83	83		
7	50th	93	93	95	96	97	99	99	55	56	56	57	58	58	59		
	90th	106	107	108	109	111	112	113	69	70	70	71	72	72	73		
	95th	110	111	112	113	115	116	116	73	74	74	75	76	76	77		
	99th	117	118	119	120	122	123	124	81	81	82	82	83	84	84		
8	50th	95	95	96	98	99	100	101	57	57	57	58	59	60	60		
	90th	108	109	110	111	113	114	114	71	71	71	72	73	74	74		
	95th	112	112	114	115	116	118	118	75	75	75	76	77	78	78		
	99th	119	120	121	122	123	125	125	82	82	83	83	84	85	86		
9	50th	96	97	98	100	101	102	103	58	58	58	59	60	61	61		
	90th	110	110	112	113	114	116	116	72	72	72	73	74	75	75		
	95th	114	114	115	117	118	119	120	76	76	76	77	78	79	79		
	99th	121	121	123	124	125	127	127	83	83	84	84	85	86	87		
10	50th	98	99	100	102	103	104	105	59	59	59	60	61	62	62		
	90th	112	112	114	115	116	118	118	73	73	73	74	75	76	76		
	95th	116	116	117	119	120	121	122	77	77	77	78	79	80	80		
	99th	123	123	125	126	127	129	129	84	84	85	86	86	87	88		
11	50th	100	101	102	103	105	106	107	60	60	60	61	62	63	63		
	90th	114	114	116	117	118	119	120	74	74	74	75	76	77	77		
	95th	118	118	119	121	122	123	124	78	78	78	79	80	81	81		
	99th	125	125	126	128	129	130	131	85	85	86	87	87	88	89		
12	50th	102	103	104	105	107	108	109	61	61	61	62	63	64	64		
	90th	116	116	117	119	120	121	122	75	75	75	76	77	78	78		
	95th	119	120	121	123	124	125	126	79	79	79	80	81	82	82		
	99th	127	127	128	130	131	132	133	86	86	87	88	88	89	90		
13	50th	104	105	106	107	109	110	110	62	62	62	63	64	65	65		
	90th	117	118	119	121	122	123	124	76	76	76	77	78	79	79		
	95th	121	122	123	124	126	127	128	80	80	80	81	82	83	83		
	99th	128	129	130	132	133	134	135	87	87	88	89	89	90	91		
14	50th	106	106	107	109	110	111	112	63	63	63	64	65	66	66		
	90th	119	120	121	122	124	125	125	77	77	77	78	79	80	80		
	95th	123	123	125	126	127	129	129	81	81	81	82	83	84	84		
	99th	130	131	132	133	135	136	136	88	88	89	90	90	91	92		
15	50th	107	108	109	110	111	113	113	64	64	64	65	66	67	67		
	90th	120	121	122	123	125	126	127	78	78	78	79	80	81	81		
	95th	124	125	126	127	129	130	131	82	82	82	83	84	85	85		
	99th	131	132	133	134	136	137	138	89	89	90	91	91	92	93		
16	50th	108	108	110	111	112	114	114	64	64	65	66	66	67	68		
	90th	121	122	123	124	126	127	128	78	78	78	79	80	81	82		
	95th	125	126	127	128	130	131	132	82	82	83	84	85	85	86		
	99th	132	133	134	135	137	138	139	90	90	90	91	92	93	93		
17	50th	108	109	110	111	113	114	115	64	65	65	66	67	67	68		
	90th	122	122	123	125	126	127	128	78	79	79	80	81	81	82		
	95th	125	126	127	129	130	131	132	82	83	83	84	85	85	86		
	99th	133	133	134	136	137	138	139	90	90	91	91	92	93	93		

* The 90th percentile is 1.28 SD, the 95th percentile is 1.645 SD, and the 99th percentile is 2.326 SD over the mean. For research purposes, the SDs in Table B1 allow one to compute BP Z scores and percentiles for girls with height percentiles given in Table 4 (ie, the 5th, 10th, 25th, 50th, 75th, 90th, and 95th percentiles). These height percentiles must be converted to height Z scores given by: 5% = -1.645; 10% = -1.28; 25% = -0.68; 50% = 0; 75% = 0.68; 90% = 1.28; and 95% = 1.645 and then computed according to the methodology in steps 2 through 4 described in Appendix B. For children with height percentiles other than these, follow steps 1 through 4 as described in Appendix B.

